### **5.5.1. Dose-Limiting Toxicity**

Toxicity is defined as dose-limiting toxicity if it meets the following criteria:

- Occurs within 6 hours after any dose for Parts A & B, or within 24 hours after any dose for Part C.
- and is considered by the Investigator to be possibly or probably related to treatment
- and, for AE or laboratory abnormality, is severe
- and, for tolerability,
  - is of Grade 3 or higher for “dermal response scoring (i)”, and
  - is Grade C, F, G, or H according to the “other effects scoring (ii)” (Section [6.3.4.1](#))

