### 3.1.4.1. Changes after review of preliminary data of n=4 from Part B by the Safety Monitoring Committee

[figure not shown]
Following the review by the Safety Monitoring Committee (see Section 5.5), changes were made to Part B for the remaining n=8 subjects, as shown in [Table 5](#).

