### **3.2.2.3. Additional preliminary data from Part B**

A population pharmacokinetic model integrating all plasma data from part A and the preliminary data from n=4 in part B lead to an estimation of the half life of 57 hours for GSK2646264. This model shows that in order to maintain a 1.8 fold margin with the  $AUC$  NOAEL to allow women of child bearing potential in the trial the doses of 180mg (10% BSA) should be administered every three days, over a total 7 day duration, rather than every day.

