#### **4.3.3.1. Showering/bathing during the study**

In all dose cohorts, subjects will be allowed to shower/bathe approximately 2 hours prior to dosing and approximately 18-22 hours following dosing. During showering/bathing the subject should only use mild, unscented, and non-medicated soap. A mild shampoo can be used for washing hair. The site of blood sampling will be protected (taped off and covered) if required, allowing the subjects to shower freely, including washing the application site(s). Subjects should refrain from rubbing the areas where the cream has been applied.

Timings of showering/bathing must be recorded (as detailed in the SPM).

Subjects must refrain from taking part in water based activities such as swimming and use of sauna/steam room for the duration of dosing until the follow-up visit.

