## **5.6. Safety Related Study Specific Dose Adjustment Criteria**

If AEs which are of severe intensity and are similar across subjects in the group, or if unacceptable pharmacological effects, reasonably attributable in the opinion of the investigator to dosing with GSK2646264, or if dose limiting toxicity (see Section 5.5.1), are observed in 2 or more subjects in dosing group 1 or dosing group 2 of part A, the dose escalation will be stopped. Relevant reporting and discussion with the GSK medical monitor and the SMC will take place. A substantial amendment will be submitted to the Ethics committees and Regulatory authorities for approval prior to any resumption of dosing.

If AEs which are of severe intensity and are similar across subjects in either Part B or C, or if unacceptable pharmacological effects, reasonably attributable in the opinion of the investigator to dosing with GSK2646264, or if dose limiting toxicity (see Section 5.5.1), are observed in 2 or more subjects in either Part B or C, relevant reporting and discussion with the GSK medical monitor and the SMC will take place.

If a Serious Adverse Event (SAE) occurs in 1 subject and is deemed to be drug related, the dose escalation in Part A, or the study if in Part B or Part C, will be stopped. Relevant reporting and discussion with the GSK medical monitor and the SMC will take place. A substantial amendment will be submitted to the Ethics committees and Regulatory authorities for approval prior to any resumption of dosing.

The above criteria will apply regardless of whether pharmacokinetics are less than the above mentioned PK stopping criteria and every effort will be made to take a blood sample at the time of the event for pharmacokinetics analysis in the presence of any of the above events.

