### 5.7.3. Safety related Stopping criteria for an individual subject

A subject may be withdrawn from the study if they present dose limiting toxicity (as defined in Section 5.5.1; also refer to tolerability assessment definition in Section 6.3.4.1.). If dose limiting toxicity is observed in an individual, the Investigator or designee may use their medical judgment and stop dosing the individual subject, and is required to immediately inform the GSK medical monitor or designee. They will then decide whether it is necessary for the SMC to be convened immediately or not, for review of the data and decision on dose adjustment or withdrawal of the individual subject.

A subject may be withdrawn from the study if they present a Serious Adverse Event (SAE), regardless of its severity, and reasonably attributable in the opinion of the investigator to dosing with GSK2646264.

A subject will be withdrawn if they require concomitant medications listed in Section 5.15.

Dosing to an individual may be stopped due to unacceptable local tolerability as evidenced by dose limiting toxicity (as defined in Section 5.5.1).

Tolerability assessments on treated skin areas will be made using the criteria in Section 6.3.4.1.

In the presence of any of the above events, every effort will be made to take a blood sample at the time of the event for pharmacokinetics analysis.

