### 6.1.3. Part B: Cold urticaria Subjects Time and Event table

Day:	Screening	-1	1	2	3	4	Day 6 to 15	Follow-up (Day 17-19)	Notes
Visit Window (relative to Day 1)	-28 to -7 days 								1. Screening can occur on any day between 28 days and 7 days prior to Day 1 dosing.
Admission to Unit		X							
Informed Consent	X								
Demographics	X								
Complete physical	X							X	
Body weight (kg)	X								
Height (cm) without shoes	X								
Brief physical		X							
Medical/medication/drug/alcohol history	X								
12-lead ECG	X 	X			X			X	2. Triplicate ECG at screening and CV risk factors
Vital signs 	X	X	X	X	X		X	X	3. Should be performed at the same time points as PK samples are taken
Urine drug/alcohol screen	X	X							
Pregnancy Test (women) 	X(S)		X(S/U)			X (S)	X(S)		4. Pregnancy test will be performed 3 times during screening, serum on day -28, day -7 to -4, and a serum or urine pregnancy test the day of the start of the study prior to dosing and a serum pregnancy test between day 10-12 (to coincide with a PK sample) and at the follow up visit.
HIV, Hep B and Hep C screen	X								
Clinical Laboratory Tests	X	X			X			X	

Day:	Screening	-1	1	2	3	4	Day 6 to 15	Follow-up (Day 17-19)	Notes
Allergen Challenge-SPT	X 		X 		X 	X 			5. SPT- Skin Prick Test measurements will be performed ~15-20mins post challenge 6. SPT using all 4 specified allergens 7. SPT will be performed at 6 hours post dose (see Section 6.4.1), and at 24 hours post last dose on day 3 8. SPT will be performed pre-dose on Day 1
TSH, free T4, T4, T3	X					X	X 	X	9. One sample between day 10-12 to coincide with PK sample
Cold Temp Test (Temp Test 4.0)	X		X 		X 	X 			10. Pre-dose 11. 6 hours post dose 12. 24 hours post last dose on Day 3
Randomisation		X							
Tolerability Assessment			←-----X  -----→						13. Tolerability assessment at pre – and ~6 hours post-dose
AE assessment			←-----X-----→				X		
Concomitant Medication		X	←-----X-----→				X		
Pharmacokinetic Blood Sample			X 	X 	X 	X 	X 	X	14. PK blood sample taken at pre dose, 1, 4, 8, 12hr post dose 15. One PK sample to be taken 24 hours post last dose on Day 3 16. One PK blood sample per day will be taken as follows: PK samples will be obtained on the following days (± 1 day): Day 6, 9, 12, & 15.

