### **Evaluating AEs and SAEs**

#### **Assessment of Intensity**

The investigator will make an assessment of intensity for each AE and SAE reported during the study and will assign it to one of the following categories:

Mild: An event that is easily tolerated by the subject, causing minimal discomfort and not interfering with everyday activities.

Moderate: An event that is sufficiently discomforting to interfere with normal everyday activities.

Severe: An event that prevents normal everyday activities.

An AE that is assessed as severe will not be confused with an SAE. Severity is a category utilized for rating the intensity of an event; and both AEs and SAEs can be assessed as severe. An event is defined as 'serious' when it meets at least one of the pre-defined outcomes as described in the definition of an SAE.

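### In Part B the six-hour DLT window leaves out a skin reaction that arises overnight and is first seen at the Day 2 or Day 3 pre-dose score, just before cream is reapplied

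*Protocol*

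**What the plan says.** Section 5.5.1 joins its DLT conditions with 'and', so all that apply must be met. The first is timing: "Occurs within 6 hours after any dose for Parts A & B, or within 24 hours after any dose for Part C". The event must also be considered possibly or probably related to treatment. For skin tolerability it must reach dermal Grade 3 or higher together with letter C, F, G or H.

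Part B subjects are dosed once each morning on Days 1 to 3 (3.1.4). The Part B Time and Events table (6.1.3, note 13) sets the skin scoring times: "Tolerability assessment at pre – and ~6 hours post-dose".

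Two rules use the DLT label in Part B.

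- **Section 5.7.3.** If a DLT is seen in an individual, the investigator may stop dosing "and is required to immediately inform the GSK medical monitor or designee". The same section ties stopping for unacceptable local tolerability to the 5.5.1 definition.
- **Section 5.6.** DLT is one of the events which, if they "are observed in 2 or more subjects in either Part B or C, relevant reporting and discussion" with the medical monitor and the Safety Monitoring Committee (SMC).

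After the SMC reviewed the first four subjects, "changes were made to Part B for the remaining n=8 subjects" (3.1.4.1). The definition therefore still governs those eight.

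**The concern.** The pre-dose score is the last scheduled look at the skin before more cream goes on the same arms, so it is when a reaction to the previous dose matters most for the decision to redose. Under 5.5.1, a reaction that was absent at 6 hours and is present at that score lies outside the window, whatever its grade.

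Late onset is not far-fetched for a cream left in place. Section 4.3.3.1 says that "subjects will be allowed to shower/bathe approximately 2 hours prior to dosing and approximately 18-22 hours following dosing". Actual residence time is not measured, but the washing rule lets cream stay on the skin well past 6 hours.

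What is at stake is specific. Without the DLT label there is no duty under 5.7.3 to tell the medical monitor at once, and the subject does not count towards the DLT limb of the two-subject trigger in 5.6. Section 5.5.1 gives no reason for using 6 hours here and 24 hours in Part C.

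**Working it through.** The plan states no figure to reproduce. The check sets the window against the dosing and scoring schedule.

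**Inputs**
- DLT window in Part B: 6 h (5.5.1).
- Dosing: every 24 h, three doses, so two reapplications (3.1.4).
- Skin scores: pre-dose and at about 6 h (6.1.3, note 13). The Day 1 pre-dose score is a baseline and is left out.
- Subjects still under the rule: 12 − 4 = 8. At 3:1 this is 6 active and 2 placebo.

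**Each score after the first dose**

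| Score | Hours since last dose | Inside 6 h? | Inside proposed window? |
|---|---|---|---|
| Day 1, about 6 h | 6 | yes, nominally | yes |
| Day 2, pre-dose | 24 | no | yes |
| Day 2, about 6 h | 6 | yes, nominally | yes |
| Day 3, pre-dose | 24 | no | yes |
| Day 3, about 6 h | 6 | yes, nominally | yes |
| Day 4, only if scored | 24 | no | yes |

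**Results**
- Per subject, 2 of 5 scores fall outside the window (3 of 6 if skin is scored on Day 4; the table's arrow does not settle this).
- Over the remaining 8 subjects: 8 × 2 = 16 of 8 × 5 = 40 scores. In the 6 active subjects: 6 × 2 = 12 of 6 × 5 = 30. These are assessments, not events.
- Share of each dosing interval covered: 6/24 = 25%. The window closes 24 − 6 = 18 h before the pre-dose score.
- The 6 h score is approximate, so it sits on the limit and can fall just past it.

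**Does the severe-AE route in 5.6 fill the gap?** A skin DLT is defined by a grade and a letter. A severe adverse event is defined by function (Appendix 2): "Severe: An event that prevents normal everyday activities". Strong erythema with peeling and cracking (Grade 3, letter C) on the arms meets the first test, yet an investigator could reasonably rate it mild or moderate. The two routes overlap, but one does not contain the other.

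**The case against.** The strongest reply is that little hangs on the label in Part B, and much of this stands.

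- Stopping an individual is permissive even for a true DLT, and the investigator may withdraw a subject for safety at any time (4.5).
- Section 7.1.3 makes every skin reaction at DLT grade a reportable adverse event, at a lower dermal threshold and with no clock.
- Similar severe events or unacceptable pharmacological effects in two or more subjects, and a single drug-related serious event, act under 5.6 without a time limit.
- The SMC can pause enrolment or ask for safety changes (5.5).
- Subjects are in-house, and staff see them at 8 and 12 hours for PK samples and vital signs (6.1.3, notes 3 and 14).

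The 6 hours also has a visible origin: it matches the scheduled skin score and the sentinel decision point in Part A (Table 8). Part C differs in being outpatient, with skin scored at 1 to 2 hours.

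These points limit the weight of the finding but do not remove it. Adverse event reporting and discretionary withdrawal carry no duty of immediate notice, the 8 and 12 hour contacts are not skin scores, and a match to one scoring time does not explain why the other is left out.

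Some stronger readings do not hold. A reader might infer that a late reaction can never be a DLT, but one that began within 6 hours, or is judged to occur within 6 hours of the next dose, may still count; in the latter case cream has already been reapplied. A reader might infer that a missed count means a missed halt, but for two DLTs in Part B section 5.6 requires reporting and discussion only. A reader might take the 57-hour half-life (3.2.2.3) as evidence that late skin reactions are likely, but it describes plasma elimination and says nothing about when skin reacts.

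**Conclusion.** The gap is real and narrow. In Part B, a reaction at DLT grade that arises more than 6 hours after a dose and is first seen at the Day 2 or Day 3 pre-dose score is not a DLT at that score, and misses the immediate notice and the two-subject count before cream is reapplied. It affects 2 of 5 post-first-dose skin scores per subject, assuming that skin is scored on dosing days only and that pre-dose scores fall about 24 hours after the previous dose.

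How often it would matter cannot be said. The documents give no rate of late reactions, and they report that the 1% cream was well tolerated in Part A, with no clinically significant safety issues in the first four Part B subjects (3.2.3). They do not support a claim that subjects are unprotected. Part A had the same window and scoring times, but its dosing is over. The change is worth making because it is cheap and concerns a stated safety rule in a first-in-human study.

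**What to change.** In 5.5.1, for Part B, replace the 6-hour limit with: *from any dose up to and including the next scheduled pre-dose assessment, or 24 hours after the last dose*. Naming the assessment avoids an argument over a score taken a few minutes past 24 hours. The length agrees with the 24 hours already used for Part C, which is a precedent for the window but not for the scoring time.

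In 6.1.3, confirm that the in-house Day 4 assessments include a skin score. Without one, the interval after the third dose gains no scheduled look from the wider window.

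Re-read the existing scores of the first four Part B subjects under the new definition; otherwise it will differ between them and the remaining eight.

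The cost is a protocol amendment with ethics and regulatory review, and a few more notifications to the medical monitor or SMC. No visit, sample or extra staff is needed: the pre-dose score is already taken, and any Day 4 score falls while subjects are still in-house (3.1.4).

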## 5.5. Planned Dose Adjustments/Progression and Stopping criteria

The study will enrol 1 sentinel subject for Part A dosing group 1 and, Part A dosing group 2. Each sentinel subject will be dosed 1 day at least before any other subjects of their dosing group or cohort. Please refer to Section 5.6 and Section 5.7 for dose adjustments and stopping criteria.

This protocol allows some alteration from the currently outlined dosing schedule, but the maximum topically applied dose at any one time will be 10mg/cm^2 of cream (360mg of free base drug) over 3600 cm^2 (20% BSA) with, based on preclinical modeling, a 6 fold cover compared to the predicted Cmax at the NOEL (16 ng/mL) and 3.5 fold cover

compared to the predicted AUC at the NOAEL (220 ng.hr/mL), or the dose which will provide this Cmax and this AUC (See Section [3.2.2](#)).

The GSK review team will be unblinded to the randomisation code and will usually include the GSK pharmacokineticist, GSK statistician, GSK data management, GSK medical monitor, GSK study team leader, GSK Global Clinical Safety and Pharmacovigilance and GSK Clinical Matrix Team leader. Other GSK employees may be included in discussions around dose adjustments and progression if it is deemed necessary and relevant by the above mentioned team members.

The Investigator or designee, study co-ordinators and any other unit staff who have been involved in assessing subjects will remain blinded during the study; however, they will attend the start of each review meeting to update the GSK team on safety and tolerability summary from each cohort; these team members will not be part of the unblinded dose escalation discussions. The investigator and/or designee should send the relevant data to the GSK review team prior to the meeting of the Safety Monitoring Committee (SMC). The study monitor will remain blinded.

The SMC will consist of the GSK review team and the Investigator and/or designee. The SMC will:

- Approve escalation from dosing group 1 to dosing group 2 in Part A (See Section [5.5.3](#))
- Approve the selection of dosing regimen to be used in Parts B and C (See Section [5.5.3.2](#))
- Evaluate and confirm potential dose-limiting toxicities
- Pause enrolment and/or request safety-related changes to the trial protocol.

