#### 6.3.4.1. Tolerability

Tolerability will be assessed with the following skin irritation scoring system, where the score consists of a numeric score according to the dermal response scoring i), and a letter according to the other effects scoring ii), as follows:

i) Dermal response scoring:

0 = no evidence of irritation

1 = minimal erythema, barely perceptible (pink)

2 = moderate erythema (definite redness), readily visible; minimal edema or minimal papular response

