**3 = strong erythema (intense redness), or erythema and papules**

4 = definite edema

5 = erythema, edema, and papules

6 = vesicular eruption

7 = strong reaction spreading beyond test site

ii) Other effects:

Z = no other effect

A = slight glazed appearance

B = marked glazing

C = glazing with peeling and cracking

F = glazing with fissures

G = film of dried serous exudate covering all or part of the patch site

H = small petechial erosions and/or scabs

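### The tolerability rule for dose-limiting toxicity in Protocol 5.5.1 needs both a high dermal grade and a surface-change letter, so a vesicular (6Z) or spreading (7Z) reaction does not qualify on its skin score

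*Protocol*

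**What the plan says.** Protocol 5.5.1 sets a time window for a DLT (6 hours after a dose in Parts A and B, 24 hours in Part C) and requires the investigator to judge it possibly or probably related. It then gives two routes. An adverse event or laboratory abnormality must be severe. A tolerability finding must meet two sub-bullets: the first reads "is of Grade 3 or higher for “dermal response scoring (i)”, and", and the second asks for letter C, F, G or H on the other-effects scale.

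Section 6.3.4.1 defines the score as "a numeric score according to the dermal response scoring i), and a letter according to the other effects scoring ii". The top two dermal grades are "6 = vesicular eruption" and "7 = strong reaction spreading beyond test site". Letters Z, A and B (no other effect, slight glazing, marked glazing) are outside the DLT list.

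Appendix 2 defines the intensity needed for the adverse-event route: "Severe: An event that prevents normal everyday activities".

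Two provisions act on a DLT in Parts B and C:
- **One subject (5.7.3):** the investigator may stop dosing and "is required to immediately inform the GSK medical monitor or designee", who then decides whether the SMC must be convened.
- **Two subjects (5.6):** where such events "are observed in 2 or more subjects in either Part B or C, relevant reporting and discussion" with the medical monitor and the SMC follow.

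The SAP shell for Table 3.18 (Appendix 11) has a comparable category written with 'or': dermal grade 3 or more, or letter F, G or H.

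**The concern.** The two scales describe different things. The number grades erythema, oedema, papules, vesicles and spread. The letter grades surface change: glazing, cracking, fissures, exudate, erosions. An acute reaction can be at the top of the first scale with nothing to record on the second. Requiring both leaves part of the top of the sponsor's own dermal scale outside the tolerability definition.

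This is a first-in-human topical product with local tolerability among its primary endpoints. Section 5.7.3 ties stopping for unacceptable local tolerability to the 5.5.1 definition. In Part C, outpatients are re-dosed on the same skin areas on Days 4 and 7, so an unambiguous trigger matters between doses. Part A dosing is already complete, so the practical effect falls on Parts B and C.

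**Working it through.** The plan states no count of qualifying scores, so there is no figure to reproduce. The check lists every possible score and applies the rule as written.

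**Inputs** (Protocol 6.3.4.1 and 5.5.1)
- Dermal grades 0 to 7: 8 levels, of which grades 3 to 7 are 5 levels.
- Letters Z, A, B, C, F, G, H: 7 levels, of which C, F, G, H (4) are in the DLT list and Z, A, B (3) are not.

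**Rule as written**
- All scores: 8 × 7 = 56.
- Grade 3 or above: 5 × 7 = 35.
- Qualifying (grade 3 or above and C, F, G or H): 5 × 4 = 20.
- Grade 3 or above but not qualifying: 5 × 3 = 15. These are 3Z, 3A, 3B, 4Z, 4A, 4B, 5Z, 5A, 5B, 6Z, 6A, 6B, 7Z, 7A and 7B.
- Split of the 15: grades 3 to 5 give 3 × 3 = 9; grades 6 and 7 give 2 × 3 = 6.
- Grades 6 and 7 together: 2 × 7 = 14 scores, of which 2 × 4 = 8 qualify.

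**Alternatives**

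| Rule | Qualifying scores of 56 | Of 14 at grades 6–7 | Of 21 at grades 3–5 | Of 21 at grades 0–2 |
|---|---|---|---|---|
| As written | 20 | 8 | 12 | 0 |
| Grade ≥3 or C/F/G/H | 35 + 3 × 4 = 47 | 14 | 21 | 12 |
| Grade ≥3 or F/G/H | 35 + 3 × 3 = 44 | 14 | 21 | 9 |
| As written, or grade 6–7 with any letter | 20 + 6 = 26 | 14 | 12 | 0 |

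**Does the adverse-event route close the gap?** A 6Z or 7Z reaction could be recorded as a related adverse event, but it must also be severe, meaning that it stops normal daily activity. A local vesicular patch need not do that. The skin-score bullet in Protocol 7.1.3 is also written with 'and' (dermal score 2 or above, and C, F, G or H). Read literally, it does not by itself make 6Z or 7Z an adverse event. Read loosely, it makes them adverse events but not severe ones. Neither reading brings a non-severe 6Z or 7Z into the DLT definition.

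**The case against.** The strongest reply is that 'and' in 5.5.1 only lists thresholds. The outer bullets for adverse events and for tolerability are also joined by 'and', yet they must be alternatives, because one toxicity need not be both. On that view the sub-bullets are alternatives too. The reading is strained: the outer bullets each carry a limiter saying which kind of finding they apply to, and the two sub-bullets carry none. If alternatives were intended, 'or' is the word to use.

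Several other points stand, and they limit the weight of the finding:
- The consequence in Parts B and C is modest. Two DLTs lead to reporting and discussion, not an automatic stop, and stopping one subject is discretionary.
- The investigator may withdraw a subject for safety at any time (4.5). Section 5.6 has other triggers. The SMC can pause enrolment (5.5), and in-stream review is allowed (9.3.1.3).
- The protocol reports that the 1% cream was well tolerated in Part A and that the first 4 Part B subjects raised no clinically significant safety issue.
- The SAP shell is descriptive, omits letter C and does not govern DLTs. It shows that the two documents combine the same scores differently; it does not show that 'or' was meant in 5.5.1.
- A plain 'or' is broad. It would admit 0C, and grades 3 to 5 in Part C could reflect the disease, since subjects enter with 4 to 20 weals in a defined area.

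**Conclusion.** The concern holds. As written, 15 of the 35 possible scores at grade 3 or above, including 6 of the 14 at grades 6 and 7, fail the tolerability route to a DLT. A 6Z or 7Z reaction not graded severe therefore prompts neither the mandatory call to the medical monitor nor the two-subject discussion through its skin score. What is lost is the stated trigger, not all oversight.

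This rests on the conjunctive reading of 5.5.1 and on the Appendix 2 definition of severe. The counts treat every number-letter pair as possible. The documents give no frequencies, so 15 of 35 is not a miss rate. It should be fixed, because the rule omits reactions at the top of its own scale and the correction is short.

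**What to change.** In Protocol 5.5.1, replace 'and' with 'or' between the two tolerability sub-bullets. If letter C alone seems too broad, use grade 3 or above, or letter F, G or H, which is the set in SAP Table 3.18. Both versions capture every score at grades 6 and 7.

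The cost is more notifications: qualifying scores rise from 20 to 47 of 56, or to 44 with F, G and H only. Relatedness and the time window would filter disease signs in Part C, as would the SMC's duty to "Evaluate and confirm potential dose-limiting toxicities".

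If that load is unacceptable, keep the present rule and add: or grade 6 or 7 with any letter. That gives 26 of 56, covers all 14 scores at grades 6 and 7 and adds nothing at lower grades. It still leaves out the 9 scores at grades 3 to 5 with Z, A or B.

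Any version amends a safety definition mid-study, after Part A and the first 4 Part B subjects were judged under the present one. The number and letter are both part of the scheduled assessment, so the new skin-score condition can be applied to those earlier scores and the result reported. As an optional clarification, write 'or' in the skin-score bullet of 7.1.3 as well.
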